### ECG evaluations

Standard 12-lead ECGs will be performed for all patients at screening/baseline, day 1-3, day 7. ECGs measurement HR, PR, QT, QRS, and QTcF will be listed by treatment, patient and visit/time, abnormalities will be flagged. Summary statistics of raw value and change from baseline will be provided by treatment and visit/time.

Change from baseline will only be summarized for patients with both baseline and post baseline values and will be calculated as:

$$\text{change from baseline} = \text{post baseline values} - \text{baseline value}.$$

Additionally, the number and proportion of patients with abnormal values below will be summarized:

- QT > 500 ms;
- QTcF > 500 ms;
- QTcF > 480 ms;

- QTc F > 450 ms;
- QTcF changes from baseline > 30 ms;
- QTcF changes from baseline > 30 ms and QTcF > 450 ms;
- QTcF changes from baseline > 30 ms and QTcF > 480 ms;
- QTcF changes from baseline > 30 ms and QTcF > 500 ms;
- QTc changes from baseline > 60 ms;
- QTcF changes from baseline > 60 ms and QTcF > 450 ms;
- QTcF changes from baseline > 60 ms and QTcF > 480 ms;
- QTcF changes from baseline > 60 ms and QTcF > 500 ms;
- HR decrease > 25% to a HR < 50 bpm
- HR increase > 25% to a HR > 100 bpm
- PR > 220 ms.
- PR increase > 25% to PR > 220 ms
- QRS > 120 ms
- QRS increase > 25% to QRS > 120 ms

Cardiac monitoring will be performed from 1 hour before dosing and up to 48 hours after the first drug administration. Any abnormalities in the continuous monitoring (i.e., pre-dose to 48 hours) will be reported in AE eCRF page, but will not be presented separately in listings.

### **Clinical laboratory evaluations**

Due to the emergency setting of the patient, screening/baseline laboratory evaluation can be performed by locally. A central laboratory will be used for all other timepoints for the analysis of all specimens collected.

Laboratory data from all sources (central and local laboratories) will be combined. All laboratory values will be converted into International System (SI) units.

Raw values as well as absolute and relative change from baseline values for hematology, biochemistry and urinalysis (quantitative and qualitative) laboratory parameters will be summarized descriptively per time point and treatment arm.

Urinalysis parameters will be listed.

Change from baseline will only be summarized for patients with both baseline and post baseline values and will be calculated as:

$$\text{change from baseline} = \text{post baseline values} - \text{baseline value}$$

Shift tables based on normal ranges to compare baseline to the worst post-baseline value will be provided by parameter and treatment arm for hematology, biochemistry and urinary laboratory data.

A listing of all laboratory values with values flagged to show the corresponding range classifications (High, Low) relative to the laboratory reference ranges will be provided by laboratory category and treatment arm.

Normal ranges by laboratory parameter will be provided in a separate listing.

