1.3 Clinical data

1.3.1 Human safety and tolerability data

S1P receptor modulators are known to cause dose dependent transient decrease in heart rate within 2-3 h of drug intake ([Legangneux et al 2013](#), [Hoch et al 2014](#)).

Commercially Confidential Information

As of 05-Mar-2018, approximately 3279 unique subjects have been enrolled into the siponimod clinical program (inclusive of Phase 1, Phase 2 and Phase 3), of which approximately 2742 unique subjects (912 healthy volunteers, 1787 patients with MS, 43 patients with PM or DM) have received siponimod and 925 subjects (297 healthy subjects and 628 patients) have received placebo. This includes subjects who sequentially received placebo and siponimod. In addition, 1 ICH patient has been enrolled in ongoing placebo-controlled study CBAF312X2207 (this study) and 363 subjects (all healthy volunteers) were exposed to other drugs.

The cumulative exposure of clinical trial subjects to siponimod since the Development International Birth Date (DIBD) of 05-Mar-2009 is estimated to be approximately 4840 patient-years. Healthy subjects have received siponimod as single doses or as multiple doses (single doses: 0.1 mg to 75 mg, multiple doses: 0.25 mg to 20 mg). Patients with MS have received siponimod (0.25 mg to 10 mg) daily from 1 day to 73 months during the clinical development program (please see Investigators Brochure).

The safety profile of BAF312 includes the following identified risks: transient effects on heart rate and rhythm (bradyarrhythmia and 2nd degree AV block) at treatment initiation that are completely avoided by initial up-titration; liver enzyme elevation; lymphopenia due to lymphocyte redistribution (main targeted PD effect of BAF312); seizures; hypertension; macular edema; and varicella zoster (VZV) infection reactivation.

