3.7 Risks and benefits

The risk to patients in this trial must be minimized by compliance with the eligibility criteria and study procedures, close clinical monitoring, and clear instructions to the Investigator on how to manage symptomatic bradycardia if it occurs.

Bradycardic effect – Treatment initiation with BAF312 results in transient decrease in HR in a dose-dependent manner, with nadir ~3-4 h after the first dose. In a clinical study in MS patients (CBAF312A2201) without dose titration, five cases of second degree AV blocks were reported: 3/29 in the 2 mg group and 2/50 in the 10 mg group. Implementation of dose titration effectively mitigated the occurrence of bradycardic events. In this study, the dose is titrated to the target daily dose of CCI BAF312. The need to achieve fast therapeutic concentration was carefully weighed against the need to prevent bradycardic effects. Unlike ischemic stroke, in which reflex tachycardia and increased blood pressure is typically allowed to persist (to some extent) to maximize perfusion of the ischemic penumbra, in hemorrhagic stroke most supportive therapies are aimed at lowering blood pressure to minimize likelihood of acute expansion of the initial hematoma. Given this, transient bradycardia carries significantly less risk in the ICH patient population than in patients with ischemic stroke.

During the first 48 hours of treatment, all patients will be on continuous CV telemetry in Stroke Units/Neurointensive Care Units, and special attention will be given to the monitoring of the HR. In case of symptomatic bradycardia, the Investigator should follow the guidance given in [Section 6.6](#). Under those predefined conditions, BAF312 treatment must be interrupted. When the heart rate has recovered, the treatment may be started again, as judged by the Investigator.

Risk of infection - The core PD effect of BAF312 is dose-dependent reduction of peripheral lymphocyte counts to 20-30 % of baseline due to their sequestration in the lymphoid tissues. As a consequence, there is an increased risk of infections. Patients with low baseline lymphocyte count are excluded from the study. There were no reports of increased bacterial infections between drug and placebo in the MS population with S1P₁ modulators (fingolimod

and BAF312). Although the risk of infection is considered small given the short treatment duration of 14 days, in this critically-ill population this risk might be higher.

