Cases of progressive multifocal leukoencephalopathy (PML), have been reported with another S1PR modulator, fingolimod, but is extremely unlikely in this population due to the short treatment duration. Nevertheless, signs of CNS infections will be routinely monitored, promptly investigated, and treated as per standard medical practice. Although not the preferred imaging modality for PML *per se*, all study patients will have CT imaging of the brain performed at 7 and 14 days after ICH, as well as ongoing neurological examinations (see [Assessment schedule](#)). Effective diagnostic and therapeutic strategies should be employed in patients with infections.

Aspiration pneumonia – Respiratory tract infections were reported only in 3 patients with MS on BAF312 (N=235) and none on placebo (N=61). While the risk of aspiration pneumonia cannot be excluded in this population, it is not believed to be increased by BAF312 treatment. All ICH patients must be monitored in the Stroke Unit/NICU setting for at least the first 48 hours after ICH, and standard-of-care treatment interventions should be implemented in cases of aspiration pneumonia.

Urinary tract infections – In the clinical trials conducted in MS patients, the incidence of overall infections was not different between placebo and BAF312 (5% in BAF312 and 3.5% in placebo). Patients with ICH requiring urinary catheterization might be at a higher risk of urinary infections, which should be treated per the standard-of-care in the Stroke Unit/NICU.

Blood pressure – In the healthy volunteer and MS population, the blood pressure lowering effect of BAF312 was very weak upon initiation. Small elevations in blood pressure were seen with siponimod treatment. The mechanism of these effects is unclear, but is potentially the result of unopposed natural sphingosine-1-phosphate ligand stimulation of S1PR type 2/3 (S1P2/3) endothelial receptors, owing to the strong functional antagonism of S1P1 by siponimod ([Brinkmann et al 2010](#)). Even taking into account that the population for this study is likely to be older, minimal effects are nonetheless expected with this BAF312 dose and short treatment duration.

Elevated liver function tests – In the Phase 2 dose-finding study in MS patients, elevated liver function tests > 3 x ULN were noted in 4.3% of patients in BAF312 (10 mg and 2 mg) groups. However, the short treatment duration of this study will likely reduce the frequency of treatment-related liver enzyme elevations.

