ALT or AST elevation accompanied by symptoms	
 ALT or AST > 3 × ULN accompanied by (general) malaise, fatigue, abdominal pain, nausea, or vomiting, or rash, or eosinophilia
Isolated ALT or AST elevation	
 ALT or AST > 8 × ULN 5 × ULN < ALT/AST ≤ 8 × ULN 3 × ULN < ALT/AST ≤ 5 × ULN
Isolated ALP elevation	
 ALP > 2 × ULN (in the absence of known bone pathology)
Others	
 Any clinical event of jaundice (or equivalent term) Any adverse event potentially indicative of liver toxicity

Table 15-2 Actions required for Liver Events

Criteria	Actions required
Potential Hy's Law case	
ALT or AST elevation with coagulopathy	
 Discontinue the study treatment immediately
ALT or AST elevation accompanied by symptoms	
 Hospitalize, if clinically appropriate Establish causality
Isolated ALT or AST elevation > 8 × ULN	
 Complete CRFs per liver event guidance*
Jaundice	
 If confirmed, consider interruption or discontinuation of study drug
Isolated ALT or AST elevation > 5 to ≤ 8 × ULN	
 If elevation persists for more than 2 weeks, discontinue the study drug Establish causality Complete CRFs per liver event guidance*
Isolated ALT or AST elevation > 3 to ≤ 5 × ULN (patient is asymptomatic)	
 Monitor liver chemistry tests two or three times weekly
Isolated ALP elevation	
 Repeat liver chemistry tests within 48-72 hours If elevation is confirmed, measure fractionated ALP; if >50% is of liver origin, establish hepatic causality Complete CRFs per liver event guidance*
Any AE potentially indicative of liver toxicity	
 Consider study treatment interruption or discontinuation Hospitalize if clinically appropriate Complete CRFs per liver event guidance*

*Liver event guidance for CRF completion is available in the Site Operations Manual

Table 15-3 Exclusion of underlying liver disease

Disease	Assessment
Hepatitis A, B, C, E	
• IgM anti-HAV; HBsAg, IgM anti-HBc, HBV DNA; anti-HCV, HCV RNA, IgM & IgG anti-HEV, HEV RNA
CMV, HSV, EBV infection	
• IgM & IgG anti-CMV, IgM & IgG anti-HSV; IgM & IgG anti-EBV

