**Table 8-1 Notable vital signs and body weight**

Vital Sign Variable	Notable Criteria
Pulse (beats/min)	>120 bpm or < 50 bpm
Systolic BP (mmHg)	≥ 160 mmHg or ≤ 90 mmHg
Diastolic BP (mmHg)	≥ 100 mmHg or ≤ 50 mmHg
Temperature (°C)	>38.3 °C/ 101°F
Body weight (kg)	More than 7% decrease from baseline weight

Listing will be provided with vital signs results and notable values will be flagged by treatment and patients. Box plot will be presented for each of vital sign parameter over visits by treatment.

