**Table 8-2 Liver event definition**

Definition
ALT or AST > 3 × ULN and TBL > 2 × ULN without initial increase in ALP to > 2 × ULN (Potential Hy's law cases)
ALT or AST > 3 × ULN and INR > 1.5
ALT or AST > 3 × ULN
ALP > 2 × ULN
AST = Aspartate aminotransferase; also known as SGOT, ALT = Alanine aminotransferase; also known as SGPT, INR=International Normalized Ratio, ALP = Alkaline phosphatase, TBL = Total bilirubin, DBL = conjugated (direct) bilirubin.

For all patients with liver values (AST, ALT, ALP, TBL) matching the thresholds of 5xULN or any criteria of the above table ([Table 8-2](#)), single patient LFT profile graphs will be generated showing all AST, ALT, ALP, TBL lab values reported for this study and the time of study treatment for these patients a listing of patients with these liver abnormalities will be provided.

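### Measured ALT/AST, lymphocyte and blood-pressure values get no by-arm patient counts by grade or protocol threshold, so severity counts for three identified risks rest on adverse-event reporting

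*SAP*

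**What the plan says.** **The risks.** Protocol 1.3.1 lists among the identified risks "liver enzyme elevation; lymphopenia due to lymphocyte redistribution (main targeted PD effect of BAF312); seizures; hypertension; macular edema". Safety is a secondary objective in both documents.

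**Laboratory values (SAP 8.2, Clinical laboratory evaluations).** Raw values and absolute and relative change are summarized by time point and arm. The categorical output is: "Shift tables based on normal ranges to compare baseline to the worst post-baseline value will be provided by parameter and treatment arm". Listing flags are High or Low against the reference range.

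**Liver criteria (SAP Table 8-2).** The isolated transaminase bands become one criterion, above 3 x ULN. Patients who meet any criterion, or who reach 5 x ULN, get individual profile graphs, and "a listing of patients with these liver abnormalities will be provided". SAP 8.3 adds an eDISH plot. Protocol Tables 15-1 and 15-2 distinguish isolated elevations of >3 to 5, >5 to 8 and, as a separate row, "Isolated ALT or AST elevation > 8 × ULN", and they do not attach the same actions to each.

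**Blood pressure (SAP 8.2, Vital signs and Table 8-1).** Values and change from baseline are summarized by arm and visit, with box plots. For the notable criteria: "Listing will be provided with vital signs results and notable values will be flagged by treatment and patients".

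**ECG and renal criteria (SAP 8.2).** For a list of ECG cut-offs: "Additionally, the number and proportion of patients with abnormal values below will be summarized". Patients meeting the renal criteria are both listed and summarized.

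**The concern.** The SAP counts patients over thresholds for ECG and summarizes renal criteria, but states no such table for the measurements behind three identified risks. In a normal-range shift table, ALT at 1.1 x ULN and ALT at 9 x ULN fall in the same High cell, although the protocol treats the bands between them as different events. A lymphocyte count just under the lower limit and one far below it share the Low cell. For blood pressure the visible text states no by-arm categorical table at all.

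The trial is meant to judge whether the overall clinical profile warrants further development. A reader of the by-arm tables could not see how many patients per arm passed each transaminase band, how severe the lymphocyte falls were in patient numbers, or how many patients newly met a notable blood-pressure criterion. Those counts would have to be tallied by hand from listings or inferred from adverse-event tables.

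**Working it through.** The point concerns which tables are planned, so there is no stated figure to reproduce. The first three steps compare the text; the last two give a sense of size.

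**1. Planned outputs side by side (SAP 8.2 and 8.3)**

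| Measurement | Thresholds in the documents | By-arm count of patients | Other planned output |
|---|---|---|---|
| ECG | Cut-offs in SAP 8.2 | Number and proportion for each | Listing, summaries, box plots |
| Renal | Protocol Appendix 2 | Summarized | Listing |
| ALT/AST | Protocol Table 15-1 bands; SAP Table 8-2 | Low/Normal/High shift only | Continuous summaries, box plots, individual graphs, listing, eDISH plot |
| Lymphocytes | Entry limit 0.8 x10^9/L (Protocol 4.2) | Low/Normal/High shift only | Continuous summaries, box plots, listing |
| Blood pressure | SAP Table 8-1 | None stated | Continuous summaries, box plots, flagged listing |

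**2. Does adverse-event reporting fill the gap?** In part. SAP 5.2.3 summarizes treatment-emergent events by severity and arm with Clopper-Pearson intervals. SAP 8.2 tabulates events by arm, preferred term and severity, and by maximum CTCAE grade. But Protocol 9.1 makes an abnormal laboratory value an adverse event only if it causes symptoms, is judged clinically significant, or needs therapy. Protocol 8.6.3.1 keeps central total WBC and lymphocyte results from the sponsor and investigator, releasing them to the site's principal investigator only for an abnormality that might need adverse-event evaluation or change treatment. So the event tables count what was judged reportable, not what was measured.

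**3. Unscheduled values.** SAP 4.4 generally leaves unscheduled and repeat assessments out of descriptive summaries, but includes them in analyses of abnormal or worst post-baseline values and names vital signs there. SAP 8.2 specifies no such by-arm vital-sign table. An unscheduled notable blood pressure would therefore generally appear only in a listing.

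**4. Lymphocytes.** Protocol 3.7 expects a "dose-dependent reduction of peripheral lymphocyte counts to 20-30 % of baseline".
- A baseline of 0.8 falls to 0.8 x 0.20 = 0.16 up to 0.8 x 0.30 = 0.24 (all x10^9/L).
- A baseline of 1.5 falls to 0.30-0.45.
- A baseline of 2.0 falls to 0.40-0.60.

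The documents give no laboratory lower limit, so I assume L between 0.8 and 1.2. The baseline needed to stay at or above L is L divided by the remaining fraction:
- L = 0.8: 0.8/0.30 = 2.7 to 0.8/0.20 = 4.0.
- L = 1.2: 1.2/0.30 = 4.0 to 1.2/0.20 = 6.0.

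Unless many patients start that high, most BAF312 patients will sit in the Low cell, and the shift table will not separate them by depth.

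**5. Transaminases.** In the earlier MS dose-finding study, "elevated liver function tests > 3 x ULN were noted in 4.3% of patients" in the 2 mg and 10 mg groups (Protocol 3.7). With about 33 patients per arm:
- Expected number: 33 x 0.043 = 1.4.
- Chance of at least one: 1 - 0.957^33 = 0.77.
- Chance of at least two: 1 - 0.957^33 - 33 x 0.043 x 0.957^32 = 0.42.

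This is indicative only, because Protocol 3.7 expects the short treatment to reduce the frequency.

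I give no size for blood pressure: the documents state neither its variability nor a rate of notable values.

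**The case against.** The strongest defence is that the information is not lost. Safety is descriptive, about 65 patients are enrolled, and every value is listed by arm. With roughly one expected case above 3 x ULN, split bands will be nearly empty and a listing is quickly tallied. Lymphocyte reduction is the drug's main targeted effect, and a shift of the whole arm shows well in median relative change. The protocol expects minimal blood-pressure effects at this dose and duration. Table specifications are held in separate documents (SAP 1.1) and parts of the SAP are redacted, so a table may exist out of sight.

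Much of this stands, and it rules out some stronger readings:
- A reader might infer that these risks are never counted by severity between arms. SAP 5.2.3 and the adverse-event tables in SAP 8.2 do count reported events that way.
- A reader might infer that only ECG thresholds are counted. Renal criteria are summarized too.
- A reader might infer that deeper lymphopenia cannot be shown. Raw values and absolute and relative change by arm, with quartiles and extremes, will show it on average.

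What does not stand is that the event tables or summary statistics replace patient counts. The first depend on judgement and, for lymphocytes, on restricted information. The second do not say how many patients crossed a threshold. The visible laboratory and vital-signs text shows no redaction, so hidden material lowers confidence but does not answer the point.

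**Conclusion.** The concern holds in a limited form. The visible SAP does not tabulate measured ALT/AST, lymphocyte or blood-pressure values by arm by grade or protocol threshold, although it gives patient counts for ECG cut-offs and a summary for renal criteria. Severity counts for three identified risks therefore rest on adverse-event reporting, which is incomplete for laboratory values and further limited by blinding for lymphocytes.

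The consequence is a weaker safety display, not a biased efficacy result or a loss of data. For the liver it concerns perhaps one or two patients in the BAF312 arm at the earlier rate, probably fewer with short treatment. For lymphocytes it concerns most treated patients, if the fall to 20-30% of baseline occurs and the laboratory lower limit lies near the assumed 0.8-1.2 x10^9/L. The conclusion also assumes that the separate table specifications do not already contain these counts.

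**What to change.** Add the following to SAP 8.2, using all post-baseline values (scheduled, unscheduled and repeat) as SAP 4.4 already provides for abnormal and worst-value analyses:

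- **Liver:** by-arm n (%) of patients by worst post-baseline ALT/AST in the Protocol Table 15-1 bands (>3-5, >5-8, >8 x ULN), and n (%) for the other Table 8-2 criteria.
- **Lymphocytes:** in addition to the normal-range shift table, by-arm n (%) by worst post-baseline CTCAE grade, in the version used for adverse events, and n (%) below the 0.8 x10^9/L entry limit at each post-treatment visit with a count. The documents do not print the CTCAE cut-points, so the SAP should cite the version. How patients will spread across grades cannot be predicted from the documents.
- **Blood pressure:** by-arm n (%) meeting each Table 8-1 criterion after baseline, split by whether it was already met at baseline.

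Keep the listings, individual graphs, box plots and eDISH plot.

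The cost is SAP wording and a few descriptive tables from data already planned, some with sparse cells. It needs no new assessment, no protocol amendment and no change to any clinical rule. If the separate table specifications already include these counts, a sentence in SAP 8.2 saying so would be enough.

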***Liver event definition:***

The liver event criteria [Table 8-2](#) will be evaluated using clinical chemistry parameters.

**Table 8-2 Liver event definition**

Definition
ALT or AST > 3 × ULN and TBL > 2 × ULN without initial increase in ALP to > 2 × ULN (Potential Hy's law cases)
ALT or AST > 3 × ULN and INR > 1.5
ALT or AST > 3 × ULN
ALP > 2 × ULN
AST = Aspartate aminotransferase; also known as SGOT, ALT = Alanine aminotransferase; also known as SGPT, INR=International Normalized Ratio, ALP = Alkaline phosphatase, TBL = Total bilirubin, DBL = conjugated (direct) bilirubin.

For all patients with liver values (AST, ALT, ALP, TBL) matching the thresholds of 5xULN or any criteria of the above table ([Table 8-2](#)), single patient LFT profile graphs will be generated showing all AST, ALT, ALP, TBL lab values reported for this study and the time of study treatment for these patients a listing of patients with these liver abnormalities will be provided.

